9.1.10 Concomitant medication

Concomitant medication listings will include the medication name, WHO-DD preferred name, WHO-DD drug class (ATC level 2), start and end date/time, dose, route, frequency, and indication will be presented. The listing will also include references to related AEs and medical history events, if applicable.

9.1.11 IMP Exposure

Details of IMP administration of each subject will be presented in listings.

9.1.12 Clinical Laboratory Evaluations

Laboratory data will be presented using units as reported by the clinical laboratory.

Listings for each category of laboratory test [hematology, serum chemistry, urinalysis, serology, coagulation, urine drug screen and other laboratory tests (pregnancy and endocrinology)] will include test name, study visit, date and time of specimen collection, reference range, observed value, and alert flag. Separate listings will be done for abnormal on-study laboratory values and for CS on-study laboratory values.

Observed values and changes from baseline will be summarized by visit. Shifts from baseline will also be summarized.

9.1.13 Vital Signs

Listings will include study visit, date and time of measurement, and observed value. For baseline SBP and DBP, triplicate measurements as well as the mean of the triplicate measurements will be listed. Separate listings will be done for abnormal on-study vital sign values and for CS on-study vital sign values.

Observed values and changes from baseline will be summarized by visit and time point. Baseline SBP and DBP will be defined as the mean of the triplicate measurements.

Triplicate means will be programmatically calculated and will be calculated even if there are only 1 or 2 measurements available. Triplicate means will be rounded to the nearest integer.

9.1.14 Physical Examination Findings

Listings of general physical examination records and CS physical examination findings will be presented.

9.1.15 Electrocardiogram

Listings will include study visit, date and time of measurement, and observed value. Triplicate measurements as well as the mean of the triplicate measurements will be listed. A separate listing will be done for CS on-study ECGs.

Observed values and, for numeric parameters, changes from baseline will be summarized by visit and time point. Means of triplicate measurements will be summarized for numeric results. ECG interpretation will be summarized by visit, timepoint, and ECG readings.

For numeric parameters, triplicate means will be programmatically calculated and will be calculated even if there are only 1 or 2 measurements available. Triplicate means will be rounded to the nearest integer. For ECG interpretation, if at least 2 of the 3 assessments are the same value, the triplicate summary (analogous to the mean for numeric parameters) will be set to this value; however, if each assessment is different (eg, "normal," "abnormal NCS," and "abnormal CS"), the Sponsor will be notified and will provide a value for the triplicate summary of interpretation based on a review of the data.

An ECG holter monitoring listing will include assessment performed, start date/time and end date/time.

9.2 Analysis Timepoints

For Part I, the baseline value will be defined as the last non-missing evaluation prior to the first dose of IMP. For Part II, the period-specific baseline value will be the last non-missing evaluation prior to the first period-specific dose of IMP. If multiple measurements are collected at baseline with the same assessment time (or date if time is not available) then the mean of the measurements will be taken. All other analysis time points will be based on nominal visits.

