### 8.6 12-Lead Electrocardiograms

A 12-lead ECG will be recorded after the subject has been in the semi-recumbent position for a minimum of 5 minutes as presented in the Schedule of Events tables (Section 22.1. Appendix 1 and Section 22.2, Appendix 2).

A triplicate ECG will be recorded for the determination of the baseline result at pre-dose. The baseline value will be the mean of the 3 recordings. If a potentially clinically significant abnormality is noted during other ECG assessments, a triplicate ECG will be taken at that timepoint. All triplicate ECG recordings should occur at least 1 minute apart. If a subject shows an abnormal assessment at any stage, repeat measurements may be made and the abnormality followed to resolution, if required. Additional measurements may be taken as deemed necessary by the Investigator.

Any clinically significant abnormalities, including changes from baseline, will be reported as AEs.

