# **14 STATISTICS**

## 14.1 General Procedures

This section describes the sample size, analysis populations and planned analyses for PK and safety endpoints. A comprehensive statistical analysis plan (SAP) will be developed to detail the statistical methodology for all aspects of the planned analyses. The SAP will be approved after the protocol is finalized and before the database is locked. Any deviations from the analyses described below will be identified in the SAP (and subsequently the CSR). Any unplanned analyses not described in the SAP will be identified in the CSR.

Data will be listed and summarized separately for Parts I and II of the study. For Part I, data will be summarized by dosing cohort for active treatment and for all placebo subjects combined. For Part II, data will be summarized by treatment group (fed or fasted) where applicable. Continuous variables will be summarized using descriptive statistics such as means, standard deviations (SD), medians, minimums and maximums. Categorical variables will be reported as frequency counts (including number missing) and the percentage of subjects in corresponding categories. Individual subject data will be presented by subject in data listings. Data listings will include all data collected from screened subjects (i.e., subjects who sign informed consent).

For change from baseline calculations, baseline will be defined as the last measurement taken prior to dosing.

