8.7 Electrocardiogram

12-lead ECG includes the parameter ECG mean ventricular rate, PR interval, QRS duration, QT interval, QTcF interval and interpretation. 12-lead ECGs will be performed according to the schedule in APPENDIX A. Triplicate measurements will be done at baseline. If a potentially clinically significant (CS) abnormality is noted during other time points, a triplicate ECG will be taken at that time point.

ECG holter monitoring will be recorded on Day 1 from at least 2 hours pre-dose until at least 24 hours post-dose for Part I and Part II. The continuous 12-lead ECG data will be stored on secure digital memory cards for potential transfer to a central ECG laboratory as indicated for QT analyses evaluating the risk of prolonged cardiac repolarization. Whether ECG holter monitoring was performed, start date/time, and end date/time will be recorded in the eCRF.

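### SAP 9.2 averages baseline readings only when their times match, which does not fit triplicate ECGs spaced at least 1 minute apart, and no SAP sentence makes ECG baseline the triplicate mean

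*SAP*

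**What the plan says.** **General rules**
- SAP 9.2, Part I: "the baseline value will be defined as the last non-missing evaluation prior to the first dose of IMP". Part II uses the same rule within each period.
- SAP 9.2 then allows averaging in one case: "If multiple measurements are collected at baseline with the same assessment time", or with the same date where no time was recorded, their mean is used.
- Protocol 14.1, for change from baseline: "baseline will be defined as the last measurement taken prior to dosing".
- The general comments in SAP 9.1 say that, of several assessments at one nominal time point, the one nearest the nominal time enters the summary tables. Only equidistant assessments are averaged.

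**ECG rules**
- Protocol 8.6 calls for a pre-dose triplicate and states: "The baseline value will be the mean of the 3 recordings". It adds: "All triplicate ECG recordings should occur at least 1 minute apart".
- SAP 8.7: "Triplicate measurements will be done at baseline. If a potentially clinically significant (CS) abnormality is noted during other time points", a triplicate is taken there as well.
- SAP 9.1.15: "Means of triplicate measurements will be summarized for numeric results". The means are derived in programming, even from one or two readings, with no condition on their times. The section announces change-from-baseline summaries but does not define ECG baseline.

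**Comparison and declared changes**
- SAP 9.1.13 says outright that baseline systolic and diastolic pressure is the mean of the triplicate.
- SAP section 11, which lists departures from the protocol's analyses, has no entry on ECG baseline.

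**The concern.** The averaging clause in 9.2 depends on identical times, and protocol 8.6 spaces the recordings so that their times differ. If each recording carries its own time, the clause is not triggered and 9.2 selects the third recording. That contradicts protocol 8.6 without being declared in section 11.

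SAP Table 1 lists change from baseline in ECG parameters among the secondary safety endpoints, and each Part I cohort has only 6 subjects on active drug. A noisier baseline than the protocol specifies would widen the spread of those changes. It would also make the tables inconsistent: the pre-dose row would show triplicate means under 9.1.15, while the changes were taken from a different value.

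**Working it through.** The plan gives no figure on this point to reproduce. The check applies the rules to one set of readings and then sizes the difference.

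**1. The rules on the same readings.** The values are hypothetical: QTcF of 402, 410 and 418 ms at 08:00, 08:01 and 08:02.

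| Rule | Baseline |
|---|---|
| SAP 9.2 read alone, one time per recording | 418 ms |
| SAP 9.2 read alone, one time for the whole set | (402 + 410 + 418)/3 = 410 ms |
| Protocol 8.6 | 410 ms |
| Triplicate mean as derived in SAP 9.1.15 | 410 ms |

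The result under 9.2 therefore turns on how times are stored. SAP 9.1.15 lists date and time of measurement, so the fallback in 9.2 to the date alone would not normally apply. It does not say whether there is one time per recording or one per set.

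**2. Is precedence stated?** For blood pressure, yes, in 9.1.13. For ECG, no. Protocol 14.1 and the nearest-in-time comment in SAP 9.1 also lean towards a single reading. Protocol 8.6 and the sense of 9.1.15 lean towards the mean.

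**3. Size.** Assumptions, since the documents give no SD:
- Each reading has independent error with SD s around the subject's level at that time point.
- That level varies between time points within a subject, independently, with SD w.
- There is one post-dose reading.

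Variance of change, single-reading baseline: 2w² + s²(1 + 1) = 2w² + 2s².

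Variance of change, triplicate-mean baseline: 2w² + s²(1 + 1/3) = 2w² + 1.333s².

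SD ratio = √[(2w² + 2s²)/(2w² + 1.333s²)]:

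| w | Calculation | SD ratio |
|---|---|---|
| 0 | √(2/1.333) | 1.225 |
| s | √(4/3.333) | 1.095 |
| 2s | √(10/9.333) | 1.035 |

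The ratio at a given w/s does not depend on s. In absolute terms with w = 0, the SD of change is:

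| Assumed s (ms) | Single reading (ms) | Triplicate mean (ms) |
|---|---|---|
| 3 | 4.24 | 3.46 |
| 5 | 7.07 | 5.77 |
| 8 | 11.31 | 9.24 |
| 10 | 14.14 | 11.55 |

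If the three readings have errors with the same distribution, either baseline has the same expected value. The loss is then precision, not bias.

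**The case against.** The strongest reply is that the ECG-specific text already answers the question. Outside abnormal findings, the only ECG triplicate in the SAP is the one at baseline, so the triplicate-mean rule in 9.1.15 has little else to act on. It carries no same-time condition. Protocol 8.6 defines baseline as that mean, section 11 declares no departure, and a specific rule normally prevails over a general one. In 9.2, the evaluation may also mean the whole pre-dose set, and a single time recorded for the set would trigger averaging.

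Much of this stands. A reader might infer that the SAP as written fixes ECG baseline at the last single reading, or that the averaging clause can never apply. The documents support neither inference: 9.1.15 points to the mean, and how the case report form records ECG times is not shown. Nor are the other readings lost, because 9.1.15 lists all of them with their mean.

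What the reply does not supply is a sentence saying that the mean in 9.1.15 is the baseline, or that it overrides 9.2. The SAP wrote that sentence for blood pressure and not for ECG, so a programmer could reasonably fall back on the general rule.

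**Conclusion.** The concern holds as an unresolved conflict between rules. SAP 9.2 and protocol 14.1, applied literally to individually time-stamped triplicates, give an ECG baseline contrary to protocol 8.6. SAP 9.1.15 suggests the right value without stating it or giving it precedence.

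The consequence is modest. The inflation in the SD of change is at most about 22%, reached only if independent, equal-SD reading error is the sole source of variation. It falls to roughly 4 to 10% if a subject's variation between time points has an SD one to two times that of a reading. All of these rest on assumed variances.

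A reader might want to express this as wider confidence intervals for mean QTcF change. The SAP plans none for ECG: section 9.1 specifies number, mean, SD, median, minimum and maximum. The summaries are descriptive, and neither a test nor the sample size depends on the choice. It should still be corrected, because it concerns a secondary safety endpoint and could produce an undeclared departure from the protocol.

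**What to change.** Change the SAP only. In 9.1.15 or 9.2, state: *Baseline for numeric ECG parameters is the mean of the available pre-dose triplicate recordings, regardless of their individual time stamps (period-specific in Part II). This overrides the last-value rule in 9.2 and the closest-in-time rule in 9.1.*

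The cost is one sentence, settled before database lock and unblinding. The recordings are already scheduled and 9.1.15 already has the mean programmed, so no new data or derivation is needed. Protocol 8.6 already gives the ECG definition, so no protocol amendment is required.

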9.3 Methods for Handling Missing Data

No imputations of values for missing data (ie, blank, "Not Done", "Not Applicable", etc) will be performed and data presentations will reflect the data point as it appears in the case report form (CRF) or electronic data file.

10 INTERIM ANALYSES AND DATA SAFETY MONI

In Part I, there will be a review of safety data for the sentinel group in each cohort before proceeding to the next subject in the cohort. There will also be a review of the safety and PK data for each cohort before dose escalation. The safety data review will be conducted by the DRSC using stopping rules defined in Section 3.6.2.

PK parameter estimation for safety review will be performed using bioanalytical data applied with subject aliases in order to maintain the study blind. PK analysis will be performed using nominal time points. The preliminary PK results of INDV-2000 and M12 at the time of the safety review will be performed as outlined in Section 7, with the exception that nominal times will be used in the analysis instead of actual times. Mean concentration-time profiles as well as parameter summary tables of the key PK parameters (e.g. C_{max} , T_{max} , and AUCs) will be generated. PK data will not be part of the safety review.

No safety review will be performed for Part II.

11 CHANGES TO PROTOCOL-SPECIFIED ANALYSES

Protocol:	SAP:
The number and percentage of subjects reporting TEAEs will be presented overall, by MedDRA system organ class (SOC) and preferred term (PT), each in descending order of frequency (then alphabetically in case of ties).	Sentence changed to: The number and percentage of subjects reporting TEAEs (incidence) and number of TEAEs will be presented both overall and by MedDRA SOC and PT, each in descending order of frequency (then alphabetically in case of ties).
IMP-related TEAEs, treatment-emergent SAEs (TESAEs), IMP-related TESAEs, TEAEs leading to death, TEAEs leading to IMP discontinuation, and TEAEs leading to IMP interruption will be presented both overall and by SOC and PT.	TEAEs leading to death, TEAEs leading to IMP discontinuation, and TEAEs leading to IMP interruption will be listed but not summarized.
TEAEs will also be summarized by intensity within SOC and PT.	Sentence changed to: TEAEs will also be summarized by maximum severity and by maximum toxicity grade within SOC and PT
In addition, TEAEs leading to death and IMP- related TEAEs leading to death will be summarized separately by PT	Removed.
	Added: Shifts from baseline in clinically abnormal results will also be summarized.
Concomitant therapies (medications) will be collected from screening until the EOS visit or the ET visit	Concomitant medications are defined as medications taken at or after the time of first IMP dose.
The PK analysis population is defined as subjects who received at least one dose of INDV-2000 and have an adequate number of PK samples collected to derive PK parameters.	Sentence changed to : The PK population is defined as subjects who received at least one dose of INDV-2000 and have an adequate number of PK samples collected to derive at least one PK parameter. Added:
	The Food Effect PK population will be defined as the subset of Part II subjects in the PK population that have at least one evaluable PK parameter for at least one meal condition.

12 GENERAL INFORMATION RELATED TO DATA PRESENTATIONS

The formats and layouts of TFLs are provided in a separate document and are common displays. Their numbering and general content follow the International Conference on Harmonisation (ICH) E3 guidelines. Actual formats and layouts may be altered slightly from those presented as necessary to accommodate actual data or statistics. Minor format changes will not require updates to the SAP, rather they may be documented in a Note to SAP.

APPENDIX A STUDY SCHEDULE(S)

APPENDIX 1 – Schedule of Events Part I

Evaluation				clinical unit			
	Screening Days		Follow-up				
	-28 to -1	Day -1 ¹²	Day 1	Day 2	Day 3	Day 4	Day 11/EOS ¹⁰ /E7
Informed Consent	Х						
Inclusion/Exclusion Criteria	Х	Х					
Randomization		Х					
Demographics (Includes height, weight and BMI)	Х						
Medical History	Х						
Physical Examination ¹	Х	Х		Х		Х	Х
Urine Drug Screen	Х	Х					
Alcohol test	Х	X ¹³					
Serum Pregnancy Test	Х						
Urine Pregnancy Test		Х					Х
Urinalysis	Х	Х		Х			
FSH test (for post-menopausal women only)	Х						
Clinical Laboratory Assessments (Chemistry and Hematology)	Х	Х		Х		Х	Х
Serology (HIV, Hepatitis B and C)	Х						
Coagulation Panel (PT/INR)	Х						
Vital Signs ²	Х	Х	X^2	Х		Х	Х
12-Lead Electrocardiogram ^{3,4}	X ³	Х	X^4	Х		Х	Х
26 Hour Holter Monitoring ⁵			Х				
PK Sampling			Х	Х	X	Х	

Protocol No. INDV-2000-101

Version Final 1.0| 2021/03/30

Page 40 of 46

Evaluation	Screening Days		In		Follow-up		
	-28 to -1	Day -1 ¹²	Day 1	Day 2	Day 3	Day 4	Day 11/EOS ¹⁰ /ET
Drug Administration			Х				
AE Assessment		Х	Х	Х	Х	Х	Х
Concomitant Medication Assessment	Х	Х	Х	Х	Х	Х	Х
Admission to Clinical Unit		Х					
Discharge from Clinical Unit						Х	

Protocol No. INDV-2000-101

Version Final 1.0| 2021/03/30

Page 41 of 46

Evaluation		Period	1 - Dosin	g Under F	asting Con	dition	Period 2 -	Dosing a	fter High-	Fat Conto	ent Meal	Follo w-up
		In	clinical un	it	Outpati	ent visits	Inc	linical un	iit		atient sits	
	Screening Days -28 to -1	Day -1 ¹¹	Day 1	Day 2	Day 3	Day 4	Day -111	Day 1	Day 2	Day 3	Day 4	Day 10/E OS/E T ⁹
Informed Consent	Х											
Inclusion/Exclusion Criteria	X	x										
Demographics (Includes height, weight and BMI)	X											
Medical History	Х											
Physical Examination ¹	X	X		X			X		X			X
Urine Drug Screen	Х	Х					Х	-				
Alcohol test	X	X ¹²					X ¹²					
Urinalysis	Х	Х		X			Х	-	X			
Clinical Laboratory Assessments (Chemistry and Hematology)	X	x		x		x	x		x		x	X
Serology (HIV, Hepatitis B and C)	X											
Coagulation Panel (PT/INR)	Х											
Vital Signs ²	X	Х	X ²	Х		Х	Х	X	X		Х	X
12-Lead Electrocardiogram ^{3,4}	X ³	X	X^4	x			x	X^4	x			X
26 Hour Holter Monitoring ⁵			X					X				
PK Sampling ⁶			X ⁶	X	Х	X		X ⁶	X	X	X	

APPENDIX 2 - Schedule of Events Part II

Protocol No. INDV-2000-101

Version Final 1.0| 2021/03/30

Page 42 of 46

Evaluation		Period	1 - Dosing	g Under F	asting Con	dition	Period 2 -	Dosing a	fter High-	Fat Conte	ent Meal	Follo w-up
		In	clinical un	it	Outpati	ent visits	Inc	linical un	it		atient sits	
	Screening Days -28 to -1	Day -1 ¹¹	Day 1	Day 2	Day 3	Day 4	Day -1 ¹¹	Day 1	Day 2	Day 3	Day 4	Day 10/E OS/E T ⁹
Standard High-Fat Breakfast ¹⁰								х				
Drug Administration			Х					X ⁸				
AE Assessment		Х	X	X	Х	X	Х	Х	X	X	Х	X
Concomitant Medication Assessment	x	х	X	x	x	x	X	x	x	x	x	X
Admission to Clinical Unit		x					х					
Discharge from Clinical Unit				X ⁷					X ⁷			

Protocol No. INDV-2000-101

Version Final 1.0| 2021/03/30

Page 43 of 46

APPENDIX 3 – Tables for Laboratory Abnormalities

Serum *	Mild (Grade 1)	Moderate (Grade 2)	Severe (Grade 3)	Potentially Life Threatening (Grade 4)**
Sodium – Hyponatremia mEq/L	132 - 134	130 - 131	125 - 129	< 125
Sodium – Hypernatremia mEq/L	144 - 145	146 - 147	148 - 150	> 150
Potassium – Hyperkalemia mEq/L	5.1 - 5.2	5.3 - 5.4	5.5 - 5.6	> 5.6
Potassium – Hypokalemia mEq/L	3.5 - 3.6	3.3 - 3.4	3.1 - 3.2	< 3.1
Glucose – Hypoglycemia mg/dL	65 - 69	55-64	45 - 54	< 45
Glucose – Hyperglycemia Fasting – mg/dL Random – mg/dL	100 - 110 110 - 125	111 – 125 126 – 200	>125 >200	Insulin requirements or hyperosmolar coma
Blood Urea Nitrogen BUN mg/dL	23 - 26	27 - 31	> 31	Requires dialysis
Creatinine – mg/dL	1.5 – 1.7	1.8 – 2.0	2.1 – 2.5	> 2.5 or requires dialysis
Calcium – hypocalcemia mg/dL	8.0 - 8.4	7.5 - 7.9	7.0 - 7.4	< 7.0
Calcium – hypercalcemia mg/dL	10.5 - 11.0	11.1 - 11.5	11.6 - 12.0	> 12.0
Magnesium – hypomagnesemia mg/dL	1.3 – 1.5	1.1 - 1.2	0.9 - 1.0	< 0.9
Phosphorous – hypophosphatemia mg/dL	2.3 – 2.5	2.0 - 2.2	1.6 - 1.9	< 1.6
CPK – mg/dL	1.25 – 1.5 x ULN***	1.6 – 3.0 x ULN	3.1 –10 x ULN	> 10 x ULN
Albumin – Hypoalbuminemia g/dL	2.8-3.1	2.5 - 2.7	< 2.5	
Total Protein – Hypoproteinemia g/dL	5.5 - 6.0	5.0-5.4	< 5.0	
Alkaline phosphate – increase by factor	1.1 – 2.0 x ULN	2.1 – 3.0 x ULN	□ 3.1 – 10 x ULN	> 10 x ULN
Liver Function Tests –ALT, AST increase by factor	1.1 – 2.5 x ULN	2.6 – 5.0 x ULN	5.1 – 10 x ULN	> 10 x ULN
Bilirubin – when accompanied by any increase in Liver Function Test increase by factor	1.1 – 1.25 x ULN	1.26 – 1.5 x ULN	1.51 – 1.75 x ULN	> 1.75 x ULN
Bilirubin – when Liver Function Test is normal; increase by factor	1.1 – 1.5 x ULN	1.6 – 2.0 x ULN	2.0 – 3.0 x ULN	> 3.0 x ULN

Protocol No. INDV-2000-101

Version Final 1.0| 2021/03/30

Page 44 of 46

Cholesterol	201 - 210	211 - 225	> 226	
Pancreatic enzymes - amylase, lipase	1.1 – 1.5 x ULN	1.6 – 2.0 x ULN	2.1 – 5.0 x ULN	> 5.0 x ULN

* The laboratory values provided in the tables serve as guidelines and are dependent upon institutional normal parameters. Institutional normal reference ranges should be provided to demonstrate that they are appropriate.

** The clinical signs or symptoms associated with laboratory abnormalities might result in characterization of the laboratory abnormalities as Potentially Life Threatening (Grade 4). For example, a low sodium value that falls within a grade 3 parameter (125-129 mE/L) should be recorded as a grade 4 hyponatremia event if the subject had a new seizure associated with the low sodium value.

***ULN" is the upper limit of the normal range.

Hematology *	Mild (Grade 1)	Moderate (Grade 2)	Severe (Grade 3)	Potentially Life Threatening (Grade 4)
Hemoglobin (Female) - gm/dL	11.0 - 12.0	9.5 - 10.9	8.0-9.4	< 8.0
Hemoglobin (Female) change from baseline value - gm/dL	Any decrease – 1.5	1.6 - 2.0	2.1 - 5.0	> 5.0
Hemoglobin (Male) - gm/dL	12.5 - 13.5	10.5 - 12.4	8.5 - 10.4	< 8.5
Hemoglobin (Male) change from baseline value – gm/dL	Any decrease – 1.5	1.6 - 2.0	2.1-5.0	> 5.0
WBC Increase - cell/mm ³	10,800 - 15,000	15,001 - 20,000	20,001 - 25,000	> 25,000
WBC Decrease - cell/mm ³	2,500 - 3,500	1,500 - 2,499	1,000 - 1,499	< 1,000
Lymphocytes Decrease - cell/mm ³	750-1,000	500 - 749	250-499	< 250
Neutrophils Decrease - cell/mm ³	1,500 - 2,000	1,000 - 1,499	500 - 999	< 500
Eosinophils - cell/mm ³	650 - 1500	1501 - 5000	> 5000	Hypereosinophilic
Platelets Decreased - cell/mm ³	125,000 - 140,000	100,000 - 124,000	25,000 - 99,000	< 25,000
PT – increase by factor (prothrombin time)	1.0 – 1.10 x ULN**	□1.11 – 1.20 x ULN	1.21 – 1.25 x ULN	> 1.25 ULN
PTT – increase by factor (partial thromboplastin time)	1.0 – 1.2 x ULN	1.21 – 1.4 x ULN	1.41 – 1.5 x ULN	> 1.5 x ULN
Fibrinogen increase - mg/dL	400 - 500	501-600	> 600	
Fibrinogen decrease - mg/dL	150 - 200	125 – 149	100 - 124	< 100 or associated with gross bleeding or disseminated intravascular coagulation (DIC)

* The laboratory values provided in the tables serve as guidelines and are dependent upon institutional normal parameters. Institutional normal reference ranges should be provided to demonstrate that they are appropriate.

** "ULN" is the upper limit of the normal range.

Protocol No. INDV-2000-101|

Version Final 1.0| 2021/03/30

Page 45 of 46

Urine *	Mild (Grade 1)	Moderate (Grade 2)	Severe (Grade	Threatening (Grade 4)
Protein	Trace	1+	2+	Hospitalization or dialysis
Glucose	Trace	1+	2+	Hospitalization for hyperglycemia
Blood (microscopic) – red blood cells per high power field (rbc/hpf)	1 - 10	11 – 50	> 50 and/or gross blood	Hospitalization or packed red blood cells (PRBC) transfusion

The laboratory values provided in the tables serve as guidelines and are dependent upon institutional normal parameters. Institutional normal reference ranges should be provided to demonstrate that they are appropriate.

Protocol No. INDV-2000-101

*

Version Final 1.0| 2021/03/30

Page 46 of 46
